	Approximately 7 to 14 days before Day 1	Day 1 Fixed visit. No window.	Day 2 Fixed visit. No window.	Day 3, 4 or 5 Conduct visit on Day 3, 4 or 5	Day 6 Fixed visit. No window.	Day 7 Fixed visit. No window.	Day 8, 9 or 10 Conduct visit on Day 8, 9 or 10
Plasma for storage ⁶		X	X	X	X	X	X
Pharmacogenetics (PGx) sample collection (if consented)		X					
AE/SAE assessment ⁷	X	X	X	X	X	X	X
HIV-associated conditions ⁷	X	X	X	X	X	X	X
Concomitant medication review	X	X	X	X	X	X	X
Interactive web response system for central randomization	X						
VH4004280/placebo	CCI						
VH4011499/placebo							

1. To minimize delays to starting the open-label standard-of-care combination antiretroviral regimen, the screening period will be conducted in as short a time as possible and ideally within 14 days. However, if necessary, the screening period may be extended up to 28 days to allow receipt of all screening results and/or to accommodate scheduling.
2. The study requires 12 clinic visits. The visit schedule for each participant will be pre-planned and weekend, work schedules and clinic hours will be appropriately considered. At least one weekend clinic visit is required from Day 1 to Day 11.
3. Complete Physical Exam performed at Screening and Day 39/Early Discontinuation. A symptom directed physical exam will be performed at all other noted visits. Any abnormalities to be recorded as AEs. SAEs are assessed from the time of consent. Non-serious AEs are assessed from the time of first dose.
4. See Section 10.2 for details of clinical laboratory tests. Total bile acids (TBA), coagulation panel, and lipid panel (total cholesterol, HDL, LDL and triglycerides) required at Days 1, 6, 11, 25, 39/Early Discontinuation. Other clinical chemistry, hematology and urinalysis done at every visit. Fasting bloodwork is required for the lipid panel. CCI [REDACTED].
5. CCI [REDACTED]. A single PK draw will be conducted at all other visits. Refer to Section 8.5 for the collection schedule, permitted collection windows and further details.
6. Plasma samples for storage will be collected at each visit starting at Day 1, including unscheduled visits. These samples will be used when needed, such as when samples are lost or where quantity is insufficient for testing. In the event samples are not used by study completion, they will be utilized for additional research on antiretroviral resistance and/or HIV-1 disease biology/host immune response (excluding any human genetic testing).

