5. STUDY POPULATION

Prospective approval of protocol deviations to recruitment and enrollment criteria, also known as protocol waivers or exemptions, is not permitted.

Up to 42 HIV-infected adults (treatment naive) who are viremic at baseline (confirmed HIV-1 RNA \geq 3,000 copies/mL) and have CD4 T-cell counts \geq 200 c/ μ L will be recruited.

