NOTE: Test is optional and participants with negative hepatitis C antibody test are not required to also undergo hepatitis C RNA testing

31. Positive SARS-CoV-2 polymerase chain reaction test, having signs and symptoms which in the opinion of the investigator are suggestive of COVID-19 (i.e., fever, cough etc.) on Day 1, or having contact with known COVID-19 positive person/s in the 14 days prior to Day 1.

32. Creatinine clearance (eGFR) of < 50 mL/min/1.73 m² via CKD-EPI method [Delgado, 2021].

33. Alanine aminotransferase (ALT) $\geq 1.5 \times$ upper limit of normal (ULN) and / or total bilirubin $\geq 1.5 \times$ ULN (isolated bilirubin $> 1.5 \times$ ULN is acceptable if total bilirubin is fractionated and direct bilirubin $< 35\%$). A single repeat of ALT and / or bilirubin is allowed within a single Screening period to determine eligibility.

34. Any Grade 3-4 laboratory abnormality at Screening, except for a Grade 4 creatine phosphokinase (CPK) and lipid abnormalities (e.g., total cholesterol, triglycerides, etc.) will exclude a participant from the study unless the investigator can provide a compelling explanation for the laboratory result(s) and has the assent of the sponsor. A single repeat of any lab abnormality is allowed within a single Screening period to determine eligibility.

35. Any acute laboratory abnormality at screen which, in the opinion of the investigator, should preclude participation in the study of an investigational compound.

36. Any positive result for illicit drug use (e.g., cocaine, heroin) at Screening. A positive screen for marijuana/THC is not exclusionary. Refer to Section 5.3.2 for guidance to be given to the participant.

OTHER EXCLUSIONS

37. During the study, alcohol consumption will be limited to the following:

[figure not shown]
- An average weekly intake of <14 drinks for males or <7 drink for females.
- One drink is equivalent to 12 g of alcohol: 12 ounces (360 mL) of beer, 5 ounces (150 mL) of white wine or 1.5 ounces (45 mL) of 80 proof distilled spirits.

38. Regular use of drugs of abuse

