Routine Urinalysis	Specific gravity Dipstick (pH, glucose, protein, blood, ketones, bilirubin, nitrite, leukocyte esterase) Microscopic examination (if blood or protein is abnormal) to include epithelial cells, RBCs, WBCs, casts, crystals and a culture (if positive, specify pathogen).
Other Tests	
 Highly sensitive (serum or urine) human chorionic gonadotropin (hCG) pregnancy test participants female at birth Follicle-stimulating hormone, if needed to demonstrate that a female is of nonchildbearing potential (See Section 10.4) Serum or urine alcohol, cotinine, and drug screen (to include at minimum: amphetamines, barbiturates, cocaine, opiates, cannabinoids and benzodiazepines) Serology [(HIV antibody 4th generation test, hepatitis B surface antigen [HBsAg], Hepatitis B Core antibody (anti-HBc), Hepatitis B surface antibody (anti-HBs) and if indicated hepatitis B DNA (by PCR), and hepatitis C virus antibody)], with reflex to HCV RNA (by PCR) if positive)

1. Details of liver chemistry stopping criteria and required actions and follow-up assessments after liver stopping or monitoring event are given in Section 10.6. All events of ALT $\geq 3 \times$ upper limit of normal (ULN) and total bilirubin $\geq 2 \times$ ULN ($>35\%$ direct bilirubin) or ALT $\geq 3 \times$ ULN and international normalized ratio (INR) >1.5 , if INR measured, which may indicate severe liver injury (possible Hy's law), must be reported to VH/GSK in an expedited manner (excluding studies of hepatic impairment or cirrhosis). Laboratory analytes to be tested will include the routine liver panel and additional analytes [such as lactate dehydrogenase (LDH), gamma-glutamyl transferase (GGT), glutamate dehydrogenase (GLDH) and serum albumin].
2. Recommend repeat testing if CPK is elevated to ensure the result is transient or due to exercise. A history regarding use of drugs known to cause increase of CPK (such as statins), physical activity or exercise preceding the CPK evaluation should be obtained.
3. Estimated serum creatinine clearance (using the Chronic Kidney Disease Epidemiology Collaboration CKD-EPI method [Delgado, 2021].
4. at screening for eligibility determination ([creatinine clearance (eGFR) of < 50 mL/min/1.73 m²].
5. If alkaline phosphatase is elevated, consider fractionating.

10.3. Appendix 3: AEs and SAEs: Definitions and procedures for recording, evaluating, follow-up, and reporting

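### Exclusion criterion 34 excludes a Grade 3 CPK at Screening by default but exempts the more severe Grade 4 CPK

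*Protocol*

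**What the plan says.** Criterion 34 in Protocol Section 5.2 excludes "Any Grade 3-4 laboratory abnormality at Screening, except for a Grade 4 creatine phosphokinase (CPK) and lipid abnormalities". The exclusion applies "unless the investigator can provide a compelling explanation for the laboratory result(s) and has the assent of the sponsor". It then adds: "A single repeat of any lab abnormality is allowed within a single Screening period to determine eligibility".

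Criterion 35 leaves a separate discretionary exclusion: "Any acute laboratory abnormality at screen which, in the opinion of the investigator, should preclude participation in the study of an investigational compound".

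The Schedule of Activities (Section 1.3, Table 1) marks safety laboratory tests at Screening. Its footnote 4 says "Other clinical chemistry, hematology and urinalysis done at every visit", and Table 9 in Section 10.2 lists CPK under clinical chemistry. For lipids, the same footnote has the "lipid panel (total cholesterol, HDL, LDL and triglycerides) required at Days 1, 6, 11, 25, 39/Early Discontinuation", which does not include Screening. Table 9 footnote 2 says of CPK: "Recommend repeat testing if CPK is elevated to ensure the result is transient or due to exercise".

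Section 5 states: "Prospective approval of protocol deviations to recruitment and enrollment criteria, also known as protocol waivers or exemptions, is not permitted".

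**The concern.** An eligibility threshold on a graded safety test should become stricter, or at least no looser, as the grade rises. Here the CPK exception covers only the upper of the two grades that the rule addresses, so the milder result faces the higher hurdle. No clinical reason for this is given.

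Two things are at stake. A site that follows the text asks for sponsor assent, or fails the participant at Screening, for a Grade 3 CPK but not for a Grade 4. A site that assumes CPK was meant to be exempt at both grades enrols the Grade 3 participant without assent, and that participant then meets an exclusion criterion as written. SAP Section 3.1, Table 2 item 07 removes from the Per-Protocol set anyone who met an exclusion criterion, so the ambiguity can carry through to the analysis.

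**Working it through.** No statistical calculation applies. The check is a literal reading of criterion 34, followed by a search of both documents for text that would correct it.

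**Step 1: order of the grades.** Protocol Section 10.7 uses the DAIDS scale, on which Grade 3 is severe and Grade 4 potentially life-threatening. SAP Section 6.2.1 applies the same scale to laboratory values.

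**Step 2: criterion 34 applied to each CPK grade.**

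| Screening CPK | Covered by the Grade 3-4 rule? | Named in the exception? | Result under criterion 34 |
|---|---|---|---|
| Grade 1 or 2 | No | Not needed | Eligible |
| Grade 3 | Yes | No | Excluded unless a repeat is below Grade 3, or there is an explanation and sponsor assent |
| Grade 4 | Yes | Yes | Exempt, with no condition |

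The sequence eligible, excluded, exempt does not follow severity.

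**Step 3: does the rule operate?** CPK belongs to the chemistry panel and that panel is run at Screening, so it does. For lipids the phrase is ambiguous, because Grade 4 may or may not qualify the lipid abnormalities as well. This has little practical effect, because no lipid panel is scheduled at Screening.

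**Step 4: the repeat.** Criterion 34 allows one repeat to settle eligibility, and Table 9 footnote 2 separately recommends repeating a raised CPK. If the repeat value is the one that counts:

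- Grade 4 falling to Grade 3 moves the participant from exempt to excluded by default.
- Grade 3 rising to Grade 4 moves the participant from excluded by default to exempt.

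**Step 5: is it corrected elsewhere?**

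- Section 8.3.7 (study pausing rules) has a similar exception for asymptomatic Grade 4 lipid or CPK results. Its parent rule covers Grade 4 only, so the exception is coherent there and says nothing about Grade 3 at Screening.
- Table 9 footnote 2 concerns repeat testing and sets no eligibility rule for Grade 3.
- Criterion 35 can exclude a Grade 4 CPK at the investigator's discretion, but does not exempt Grade 3.

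No other text exempts a Grade 3 CPK.

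**Step 6: alternative wordings.** Exempting Grade 3-4 CPK gives eligible, exempt, exempt. Exempting Grade 3 CPK only gives eligible, exempt, excluded by default. Both follow severity.

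**Step 7: reach into the analysis.** Each active arm has 6 participants and each Part 1 placebo group has 2 (Protocol Section 4.1). Losing one participant from the Per-Protocol set therefore removes 1/6 of an active arm or 1/2 of a Part 1 placebo group. SAP Section 4.2.3 uses that set for a sensitivity analysis. SAP Section 4.2.2 bases the primary analysis on the Full Analysis Set, which item 07 does not affect.

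**The case against.** The strongest reply is that this is a drafting slip with an obvious intent and little consequence. The pausing rules tolerate an asymptomatic Grade 4 CPK, and the visible risk table in Section 2.3.1 lists no muscle or CPK risk, so the sponsor probably meant to exempt CPK at both grades. That is plausible, but the criterion does not say it.

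A Grade 3 CPK also has ways through. A repeat is allowed. Table 9 footnote 2 asks for a history of exercise and CPK-raising drugs, which could supply the explanation. Section 5.3.3 asks for 48 hours without strenuous exercise before laboratory draws. The assent route is part of criterion 34, so using it is not a prohibited waiver; the ban matters only for a site that bypasses that route. All of this stands, and it means the usual cost is a repeat or a call to the sponsor rather than loss of the participant.

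Nor is a Grade 4 CPK unchecked. Inclusion criterion 2 requires overt health on an evaluation that includes laboratory tests, and exclusion criteria 7 and 35 leave room for investigator judgement. That also stands, but none of these requires the sponsor assent demanded for the milder result.

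The repeat scenario is conditional, since a literal reader has no eligibility reason to repeat an exempt Grade 4 value. The Per-Protocol consequence needs a chain of events: a Grade 3 result, no qualifying repeat, no assent, and enrolment anyway. Both points limit the impact. Neither removes the inversion.

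**Conclusion.** The concern holds. Read as written, criterion 34 is stricter for Grade 3 CPK than for Grade 4, and neither document corrects it. It is an operative eligibility rule and should be amended, although its practical weight is modest.

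For Grade 3, enrolment requires a repeat below Grade 3, or an explanation together with sponsor assent. For Grade 4, criterion 34 requires nothing. The number of participants affected cannot be estimated, because the documents give no frequency of Grade 3-4 CPK at Screening. The primary analysis is unaffected, and any analytic consequence is confined to the Per-Protocol sensitivity analysis.

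The conclusion rests on a literal reading. The reversal on repeat testing further assumes that the repeat value decides eligibility, which the wording suggests but does not state outright.

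**What to change.** Amend criterion 34 so that the exception does not skip the lower grade. There are two coherent options:

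- If CPK is not meant to be exclusionary, write *except for Grade 3-4 CPK and Grade 3-4 lipid abnormalities*. This also settles the lipid ambiguity.
- If Grade 4 CPK should need an explanation and sponsor assent, exempt Grade 3 CPK only, and state separately which lipid grades are exempt.

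Which one applies is the sponsor's clinical decision. The Grade 4-only exception in Section 8.3.7 should not serve as the model, because under a Grade 3-4 rule it reproduces the same inversion.

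The change is one sentence in the protocol, with no cost in data or analysis. The SAP needs no edit, since Table 2 item 07 refers to the criteria generally.

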5.3. Lifestyle considerations**5.3.1. ~~CCI~~ and dietary restrictions**

Participants will be required to fast for at least 8 hours (overnight) prior to the morning check-in for the Days 1, 6, 11, 25, and 39/Early Discontinuation Visits. Blood work for the safety labs and HIV-1 RNA will be drawn at the beginning of any clinic visit and, when applicable, before consumption of any ~~CCI~~ and dosing.

~~CCI~~

Refrain from excessive consumption of red wine, Seville oranges, grapefruit or grapefruit juice, pomelos, exotic citrus fruits, grapefruit hybrids, or fruit juices from 3 days prior to the first dose of study medication through the Day 11 visit. Excessive consumption is defined as more than one glass of red wine or juice or one fruit per day, in combination.

5.3.2. Caffeine, alcohol, tobacco, marijuana/THC and illicit drug use

- During the study alcohol consumption will be limited to the following: An average weekly intake of <14 drinks for males or <7 drinks for females. One drink is equivalent to 12 g of alcohol: 12 ounces (360 mL) of beer, 5 ounces (150 mL) of wine or 1.5 ounces (45 mL) of 80 proof distilled spirits.
- No alcohol will be consumed for the intensive PK days (~~CCI~~ ██████████ until after the final assessment of the day and release from the clinic.
- No caffeine or xanthine containing products (e.g., coffee, tea, cola drinks, and chocolate) will be consumed for the intensive PK days (~~CCI~~ ██████████

██████████ until after the final assessment of the day and release from the clinic.

- Only clinically minor to moderate use (as determined by the investigator) of tobacco or nicotine containing products will be allowed during study participation, with extremely limited use on the intensive PK days ██████████ until after the final assessment of the day and release from the clinic.
- Any positive result for illicit drug use (e.g., cocaine, heroin) at Screening is exclusionary. A positive screen for marijuana / THC is not exclusionary. Participants should refrain from the use of marijuana from Day 1 through the Day 11 visit.

5.3.3. Activity

Participants will abstain from strenuous exercise for 48 hours before each blood collection for clinical laboratory tests. Participants may participate in light recreational activities during studies.

5.4. Screen failures

Screen failures are defined as participants who consent to participate in the clinical study but are not subsequently enrolled (i.e., not subsequently randomized to study intervention). A minimal set of screen failure information is required to ensure transparent reporting of screen failure participants to meet the Consolidated Standards of Reporting Trials (CONSORT) publishing requirements and to respond to queries from regulatory authorities. Minimal information includes demography, screen failure details, eligibility criteria, any protocol deviations and any serious adverse events (SAEs).

Individuals who do not meet the criteria for participation in this study (screen failure) may be rescreened. Rescreened participants should be assigned a new participant number. Previously assigned participant numbers are to be recorded in the participants' eCRF.

5.5. Criteria for temporarily delaying enrollment/randomization

Refer to Section 7.1 for safety criteria that could temporarily pause further recruitment into the study.

6. STUDY INTERVENTIONS AND CONCOMITANT THERAPY

The definition of study intervention is provided in [Table 3](#) and includes VH4004280/placebo [CCI](#) and VH4011499/placebo [CCI](#). Study intervention does not include locally sourced open-label SOC that is first administered at the end of the Day 11 visit and after final collection of the primary endpoint data (Day 11 plasma HIV-1 RNA sample).

6.1. Study interventions administered

Table 3 Study interventions administered

Intervention Label	VH4004280 CCI	Matched placebo for VH4004280 CCI	VH4011499 CCI	Matched placebo for VH4011499 CCI
Intervention Name	VH4004280 CCI	Matched placebo for VH4004280 CCI	VH4011499 CCI	Matched placebo for VH4011499 CCI
Intervention Description	CCI			
Type	Drug	Drug	Drug	Drug
Dose Formulation	Tablet	Tablet	Tablet	Tablet
Unit Dose Strengths	CCI			
Route of Administration	Oral	Oral	Oral	Oral
Use	Experimental	Placebo	Experimental	Placebo
IMP and NIMP/AxMP	IMP	IMP	IMP	IMP
Sourcing	Provided centrally by the sponsor	Provided centrally by the sponsor	Provided centrally by the sponsor	Provided centrally by the sponsor
Current Alias	GSK4004280	Not applicable	GSK4011499	Not applicable

Table 4 VH4004280 study arms

Arm Title	VH4004280	VH4004280	Placebo for VH4004280	VH4004280	Placebo for VH4004280
Part	Part 1a	Part 1a	Part 1a	Part 2a	Part 2a

Arm Title	VH4004280	VH4004280	Placebo for VH4004280	VH4004280	Placebo for VH4004280
Arm Type	Experimental	Experimental	Placebo	Experimental	Placebo
Regimen	1	2	3	4	5

CCI

¹ Doses in Part 2 may be adjusted based on preliminary analyses of exposure and response data from Part 1. As a result, the dosing instructions and the placebo match in Part 2 would then be aligned to the specific dose regimen that is chosen.

Table 5 VH4011499 study arms

Arm Title	VH4011499	VH4011499	Placebo for VH4011499	VH4011499	Placebo for VH4011499
Part	Part 1b	Part 1b	Part 1b	Part 2b	Part 2b
Arm Type	Experimental	Experimental	Placebo	Experimental	Placebo
Regimen	6	7	8	9	10

CCI

¹ Doses in Part 2 may be adjusted based on preliminary analyses of exposure and response data from Part 1. As a result, the dosing instructions and the placebo match in Part 2 would then be aligned to the specific dose regimen that is chosen.

6.2. Preparation, handling, storage, and accountability

- The investigator or designee must confirm appropriate conditions (e.g., temperature) have been maintained during transit for all study intervention received, and any discrepancies are reported and resolved before use of the study intervention.
- Only participants enrolled in the study may receive study intervention, and only authorized site staff may supply, prepare, or administer study intervention
- All study intervention must be stored in a secure, environmentally controlled, and monitored (manual or automated) area in accordance with the labeled storage conditions with access limited to the investigator and authorized site staff.
- The investigator or authorized site staff are responsible for study intervention accountability, reconciliation, and record maintenance (i.e., receipt, reconciliation, and final disposition records).
- Further guidance and information for the final disposition of unused study interventions are provided in the Pharmacy Manual.
- Under normal conditions of handling and administration, study intervention is not expected to pose significant safety risks to site staff.
- A MSDS/equivalent document describing occupational hazards and recommended handling precautions either will be provided to the investigator, where this is required by local laws, or is available upon request from VH/GSK.

6.3. Assignment to study intervention

All participants will be centrally assigned to randomized study intervention using an IWRS. Before the study is initiated, the log-in information and directions for the IWRS will be provided to each site. [CCI](#) [REDACTED]

[REDACTED]. Unused study intervention tablets in opened bottles may not be offered to the study participant beyond the expected dosing schedule as outlined in the SoA (Section 1.3) and may not be offered to any other person.

6.4. Blinding

This is a double-blind (sponsor unblinded) placebo-controlled study in which participants/investigators will not be unblinded to treatment (active capsid inhibitor drug or placebo) at the participant level. [CCI](#) [REDACTED]

CCI

There is a theoretical concern that investigators may deduce treatment assignment during the monotherapy period since they will have access to HIV-1 RNA results from the monotherapy period. However, since this study is a proof-of-concept clinical trial rather than a confirmatory trial, insufficient anti-viral effect over the monotherapy period cannot reliably predict placebo assignment. The monotherapy period is short which minimizes the likelihood of bias on subsequent endpoints during the monotherapy period. Knowledge of the treatment received during the monotherapy period is of little consequence within the SOC period and has no impact on the future conduct of the trial or assessment of study endpoints.

The IWRS will be programmed with blind-breaking instructions. In case of an emergency, the investigator has the sole responsibility for determining if unblinding of a participants' intervention assignment is warranted. Participant safety must always be the first consideration in making such a determination. If the investigator decides that unblinding is warranted, the investigator may, at the investigator's discretion, contact VH/GSK to discuss the situation prior to unblinding a participant's intervention assignment unless this could delay emergency treatment for the participant. If a participant's intervention assignment is unblinded, VH/GSK must be notified within 24 hours of this occurrence. The date and reason for the unblinding must be recorded.

If the investigator is unable to access the IWRS they can contact the GSK helpdesk based on the information provided in the pharmacy manual. A physician other than the investigator (e.g., an emergency room physician) or participant/participant's caregiver or family member may also request emergency access to the participant's study intervention information as per participant card.

The blinding strategy for this study is further structured to ensure that no one at VH/GSK who is involved in the management of individual participants is unblinded to treatment at the participant level. As a general principle during study conduct, members of the VH/GSK study team and other VH/GSK staff will remain blinded to the assignment for individual participants aside from where unblinding is necessary to support the informal planned interim analyses or becomes necessary for safety reasons.

Refer to Section 9.5 for more details about preservation of the blind during the conduct of the informal planned interim analyses. VH/GSK global safety staff may unblind the intervention assignment for any participant with an SAE. If the SAE requires that an expedited regulatory report be sent to one or more regulatory agencies, a copy of the report, identifying the participant's intervention assignment, may be sent to investigators in accordance with local regulations and/or VH/GSK policy. A participant may continue in the study if that participant's intervention assignment is unblinded.

